8.5.5. Safety Monitoring for Blood Pressure

If the patient is symptomatic (i.e., dizziness, light-headedness, clammy skin, fatigue, blurry vision), at any point in the study, the patient should contact the Study Center immediately or should a patient experience a BP measurement of ≤ 90 mmHg (systolic) 2 additional measurements must be done within a 30-minute period. If the confirmed average of the 2 additional SBP measurements is ≤ 90 mmHg and/or the patient remains symptomatic, dosing of a patient with Study Drug will be paused. Oral and/or IV hydration should be instituted. The suitability of the patient for continued dosing will be determined by the Investigator in consultation with the Sponsor Medical Monitor after the SBP has normalized and/or patient is no longer symptomatic and will be based on the reversibility of initiating factors (e.g., decreased oral intake, cold/flu, other illness). If the patient remains symptomatic or if the SBP does not normalize Study Drug should be permanently discontinued (refer to Section 8.6.6).

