10.6.2. Safety Analysis

The safety analysis will be conducted on the Safety Population.

Treatment duration and amount of Study Drug (ISIS 757456 or placebo) received will be summarized by treatment group. Patient incidence rates of all AEs will be tabulated by MedDRA™ system organ class, and by Preferred Term. Narratives of treatment emergent deaths, SAEs and AEs of special interest, including early withdrawals due to AEs, will also be provided.

All treatment-emergent AEs and SAEs as well as all treatment-emergent AEs and SAEs potentially related to Study Drug (ISIS 757456 or placebo) will be summarized.

Laboratory tests to ensure patient safety including chemistry panel, complete blood count with differential, coagulation panel, complement etc., will be summarized by study visits for each treatment group. These safety variables will also be presented as change and percent change

from Baseline over time after Study Drug (ISIS 757456 or placebo) administration, as appropriate.

Vital sign and ECG measures will be tabulated by treatment group. In addition, the number of patients who experience abnormalities in clinical laboratory evaluations will be summarized by treatment group.

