1.3.3. Safety Endpoints

Incidence and severity of treatment-emergent adverse events (TEAE), use of concomitant medications, abnormal findings in laboratory assessments, electrocardiogram (ECG), and vital signs

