In general, all post-baseline data will be summarized using the visit labels provided in the data. Multiple results with the same visit label will be averaged for continuous variables, and the worst result will be used for categorical variables. Results with visit labels as "Unscheduled" will not be included in by-visit summary tables and figures except for determining baseline and the incidence of abnormality lab summary including, but not limited to, AST, ALT, potassium, eGFR, urine protein/creatinine ratio, and platelet specified in Section 3.7.4, but will be presented in data listings. Other situations, such as required additional confirmation, will be described separately in the related endpoint analysis approach.

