A confirmed value is based on a consecutive lab value performed on a different day to, but within 7 days of, the initial value. If there are multiple results on the same day, no matter from the same lab vendor or different lab vendors, then the worst value will be utilized in the analysis. If the repeated value is in the same or worse category, then the initial value is considered confirmed. If the consecutive value is in a better category, then the initial value is confirmed using the consecutive value category. If values that are not confirmed due to failure to retest or missing lab values, then the initial value is presumed confirmed.

Additional analysis to explore the possible thrombocytopenia incidence can also be found in AESI described in Section 3.7.2.

Subjects with more than one confirmed value will be counted exactly once under the worst confirmed category.

3.7.4. 2.12.4 Vital Signs

Vital signs include heart rate, respiratory rate, body temperature, BMI and systolic and diastolic blood pressure. Except for systolic and diastolic blood pressure, which are efficacy endpoints for this study and will be summarized separately, other vital signs will be summarized by treatment group for vital sign values as well as the change and percent change from baseline at each post-Baseline visit.

3.7.5. 12-Lead Electrocardiograms (ECG)

Safety 12 lead ECG will be performed at the visits indicated in the protocol Schedule of Procedures.

The ECG data will include ventricular rate (VR), PR interval, QRS duration, QT, and corrected QT intervals (QT corrected using the Fridericia's formula), and overall interpretation.

For the continuous variables above, descriptive statistics (n, mean, standard error, standard deviation, median, 25th percentile, 75th percentile, minimum and maximum) of results at study screening and study Week 13 visit, as well as the change and percent change from Baseline, will be presented in summary tables; for the categorical responses to overall interpretation.

All the ECG data collected will be listed.

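### The SAP specifies no Safety Set count of patients whose measured blood pressure meets the protocol's own monitoring and stopping thresholds

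*Combined protocol and SAP*

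**What the plan says.** The safety endpoint (Protocol 1.2.3, SAP 1.3.3) includes "abnormal findings in laboratory assessments, electrocardiogram (ECG), and vital signs". Protocol 10.6.2 says "Vital sign and ECG measures will be tabulated by treatment group" and makes no exception for blood pressure; Protocol 10.6 places safety assessments on the Safety Set.

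SAP 3.7.4 lists systolic and diastolic pressure among the vital signs and then removes them from the summary: "Except for systolic and diastolic blood pressure, which are efficacy endpoints for this study and will be summarized separately".

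Under Analytical Visits in SAP 3.2.1, results labelled as unscheduled "will not be included in by-visit summary tables and figures except for determining baseline and the incidence of abnormality lab summary". They are not discarded: "but will be presented in data listings". The same paragraph sets the rule for repeats: "Multiple results with the same visit label will be averaged for continuous variables, and the worst result will be used for categorical variables".

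SAP 3.7.2, in the adverse-event section, promises a summary of hypotension and hyperkalemia incidence without saying how either is defined.

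Protocol 8.5.5 requires two repeat measurements within 30 minutes after an SBP of 90 mmHg or less, and attaches a dosing consequence: "If the confirmed average of the 2 additional SBP measurements is" at or below 90 mmHg. Protocol 8.6.6 and Table 7 apply the same two-repeat confirmation to SBP > 180 or DBP > 115 mmHg.

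**The concern.** Hypotension is the first risk in Protocol Table 1, and both low and high pressure have numeric rules that can pause or end dosing. That blood pressure is also an efficacy endpoint does not end its role as a safety measurement. An efficacy table cannot do the safety job: an SBP of 85 mmHg counts there as a fall from baseline and as a systolic goal reached.

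Followed exactly, the SAP produces no table from which a reader could compare 80 mg, 120 mg and placebo on how many patients had a measured pressure meeting the protocol's thresholds. The unscheduled-result rule adds to this. Protocol 8.5.5 tells symptomatic patients to contact the site at once, so some of the readings that matter most may be taken outside scheduled visits.

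**Working it through.** The plan gives no figure to reproduce. The check traces every SAP output that could carry an on-study blood pressure value and asks whether it gives a per-group count of patients at the protocol thresholds.

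| SAP output | What it shows | Count at SBP ≤ 90, SBP > 180 or DBP > 115? |
|---|---|---|
| 3.4.1, items 8 and 9 | SBP and DBP change by scheduled visit, PPS and FAS | No |
| 3.4.1, items 3, 6 and 7 | Goal rates at 140/90 and 130/80 | No |
| 3.2.1 descriptive statistics | Minimum and maximum by group | No, shows the most extreme value only |
| 3.4.1 spaghetti plots | Individual courses by group | No, visible but not counted |
| 3.7.2 hypotension summary | Incidence, undefined | Not specified for low SBP; high BP not covered |
| 3.7.2 TEAE tables | Coded events | No |
| 3.2.4 and 3.7.6 | Discontinuation reasons; newly started HTN medication | No |
| 3.7.3 | Liver enzymes, potassium, platelets, eGFR, UPCR | Thresholds counted, but not for BP |
| 3.7.4 | Vital signs other than SBP and DBP | Excluded |
| Listings | All readings, including unscheduled | No |

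**Unscheduled readings.** The exception in 3.2.1 covers baseline and the laboratory abnormality summary. Every parameter it names is a laboratory test. It points to Section 3.7.4, which is the vital-sign section, while the laboratory categories stand in 3.7.3. This looks like a wrong cross-reference and does not extend the exception to blood pressure.

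**Hypotension against hyperkalemia.** SAP 3.7.2 names both in one sentence. Potassium also has a table of measured values in 3.7.3; blood pressure has no counterpart.

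**Does averaging hide a confirmed event?** Let x be the triggering SBP and m the mean of the two repeats. If x ≤ 90 and m ≤ 90, the mean of the three is (x + 2m)/3 ≤ (90 + 180)/3 = 90. The same argument holds above 180: (x + 2m)/3 > (180 + 360)/3 = 180. Averaging the three readings therefore cannot conceal a confirmed event. Only further readings under the same visit label could. With assumed readings of 86, 88 and 90 the mean is 264/3 = 88.0; adding later readings of 104 and 106 gives 474/5 = 94.8.

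**Group sizes.** Each dose group: 150 × 1/2 × 2/3 = 50. Pooled placebo: 2 × (150 × 1/2 × 1/3) = 50. One patient is 1/50 = 2% of a group.

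**The case against.** The strongest case for the plan is that the readings are neither lost nor invisible. Unscheduled values are listed. Minimum and maximum values and individual plots are planned by group. The FAS should contain any dosed patient with a post-baseline office SBP, so its difference from the Safety Set matters little for scheduled readings. By-visit SBP and DBP changes run through the post-treatment visits, so a mean rise after dosing ends would show. All of this stands. None of it gives the number of patients affected per group.

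A reader might infer several stronger points that the documents do not support:

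- That low pressure is counted nowhere in the safety analyses. The hypotension summary in SAP 3.7.2 falls under the Safety Set analyses. Its place among adverse events suggests coded terms, but the SAP does not say so; it is undefined, not absent.
- That averaging hides confirmed events. The algebra above shows that it does not for the triggering reading and its two repeats, and 3.2.1 uses the worst result for categorical variables. The cause is that no blood pressure category is specified.
- That blood pressure appears only as efficacy means, changes and goal rates. Extremes can also be seen in the minimum and maximum, the plots and the listings.
- That comparison of this risk rests on adverse-event coding alone. Discontinuation reasons and newly started antihypertensives are also summarised by group.
- That the gap can be sized by how far a few large falls move a group mean. Such a shift reflects real falls in pressure and would be the same with or without a safety table.

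**Conclusion.** The point holds as a gap in specified reporting. SAP 3.7.4 departs from Protocol 10.6.2 by removing blood pressure from the safety vital signs. With the unscheduled rule in 3.2.1, this leaves the protocol's low and high thresholds without a specified Safety Set count. The high-pressure criterion has no counterpart at all; the low-pressure one has a summary that cannot be interpreted until it is defined.

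The size is best stated as what is missing: a per-group number and percentage for each criterion, where each patient is about 2 percentage points. How many patients would be affected cannot be derived from the documents. The primary analysis, power and type I error are untouched. It should be corrected because the measurements are already collected and the remedy is cheap.

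This rests on reading the SAP as written. If the table shells already define the hypotension summary from measured pressure, the low-SBP part shrinks to a wording change, and the high-pressure part remains. The documents also do not say which visit label a confirmatory or symptomatic reading carries, so the share falling under the unscheduled rule is unknown.

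**What to change.** - **SAP 3.7.4:** keep the by-visit blood pressure summaries in the efficacy section. Add one Safety Set table, by treatment group, giving the number and percent of patients with any post-baseline reading, scheduled or unscheduled, of SBP ≤ 90 mmHg, and of SBP > 180 or DBP > 115 mmHg. Show also those confirmed as in Protocol 8.5.5 and 8.6.6. Cover both the Treatment and the Post-Treatment Periods.
- **SAP 3.2.1:** add blood pressure to the exception for unscheduled results, and correct the section reference for the laboratory categories while the sentence is open.
- **SAP 3.7.2:** state whether the hypotension summary uses adverse-event terms, and which, or measured pressure.

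Deleting the exclusion in 3.7.4 would not be enough, because a by-visit table of means counts no threshold events. The thresholds are those already in the protocol, and no clinical rule changes. The cost is SAP wording and one table from data already collected, with blood pressure then shown in both the efficacy and safety sections.

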3.7.6. Prior and Concomitant Medications

Prior and Concomitant medications will be coded using WHO Drug dictionary (Global B3 March 2021) and summarized by ATC class, generic name and treatment group.

Prior medications include medications that started prior to the first dose of study medication regardless of whether they continued while on treatment or not. Concomitant medications include medications that patients are exposed to on or after the first dose of study medication.

Additional summary of HTN medications uses at baseline and new initiation of HTN medication during the study will be summarized by ATC class and treatment group.

Listings will be provided.

APPENDIX 1. EQ-5D HEALTH STATE INDEX SCORE DERIVATION ALGORITHM

To derive this index value, the response of each dimension will be first translated into a weight based on the value sets issued by EuroQoL group (see table x). The index value then can be calculated as **1- sum of weights from these 5 dimensions' response**. The possible best value is 1 for both regions and the possible worst value is -0.285 for UK region and -0.573 for US region. If there is a missing response from a dimension, then the index value will not be calculated and be treated as missing. For this study, all the other non-US counties will utilize UK county weight instead. The display of the index value is with 3 digits of decimal points.

Table 1: Weight of EQ-5D-5L Response by Region

				EQ-5D-5L Dimension		
Region	Response	Mobility	Self- Care	Usual Activities	Pain/ Discomfort	Anxiety/ Depression
UK	1) No problem	0	0	0	0	0
(16/11/2020)	2) Slight problem	0.058	0.05	0.05	0.063	0.078
	3) Moderate problems	0.076	0.08	0.063	0.084	0.104
	4) Severe problems	0.207	0.164	0.162	0.276	0.285
	5) Unable to	0.274	0.203	0.184	0.335	0.289
US	1) No problem	0	0	0	0	0
(16/11/2020)	2) Slight problem	0.096	0.089	0.068	0.06	0.057
	3) Moderate problems	0.122	0.107	0.101	0.098	0.123
	4) Severe problems	0.237	0.22	0.255	0.318	0.299
	5) Unable to	0.322	0.261	0.255	0.414	0.321

Sources: https://euroqol.org/support/tools/analysis-tools/index-value-set-calculators/

Version:	1
Version Date:	18 Aug 2022
Title:
